# at baseline)66

- Dispense of study medication (BAY 1163877) and diary
- → Oral administration of BAY 1163877
- Toxicities / AE assessment and recording (if applicable)

 Modified by Amendment 7, see section 15.6.2.22

No. BAY 1163877 / 16443

17 Oct 2018 Version 8.0 Page: 78 of 395

#### Day $8 \pm 1$ (Visit)

- Update of concomitant therapy
- Physical examination
- Ask subject for changes in vision
- Cardiovascular assessment (BP and HR)
- Measurement of body temperature
- ECOG performance status
- Blood and urine collection for safety laboratory tests (repetitions for controls may be necessary), for details see Section 16.2.
- Only for subjects in Part 3: Collection of peripheral blood for determination of cytokine levels 67
- Calculation of eGFR (see Section 16.9)
- Dispense of study medication (BAY 1163877) and diary
- → Oral administration of BAY 1163877
- Toxicities / AE assessment and recording (if applicable)

#### Days 15 (Visit)

- Update of concomitant therapy
- Physical examination
- Ask subject for changes in vision
- Cardiovascular assessment (BP and HR)
- Measurement of body temperature
- ECG reading (see Section 9.5.3.4)
- ECOG performance status
- Blood and urine collection for safety laboratory tests (repetitions for controls may be necessary), for details see Section 16.2.
- Calculation of eGFR (see Section 16.9)
- PK sampling (all subjects of study Part 1, 3 and at least 12 subjects of study Part 2 and approximately 8 subjects of the MTD expansion cohorts with impaired renal function

 Added by Amendment 7, see section 15.6.2.22

No. BAY 1163877 / 16443

17 Oct 2018 Version 8.0 Page: 79 of 395

#### at baseline)68

- Dispense of study medication (BAY 1163877) and diary
- → Oral administration of BAY 1163877
- Toxicities / AE assessment and recording (if applicable)

#### 9.1.2.3.2 Subsequent Cycles (Cycles 2-12) - amended

#### Day 1 (Visit)

- Update of concomitant therapy
- Physical examination
- Ask subject for changes in vision
- Cardiovascular assessment (BP and HR)
- Measurement of body temperature and body weight
- 12-lead ECG, single reading (see Section 9.5.3.4)
- ECOG performance status
- Blood and urine collection for safety laboratory tests (repetitions for controls may be necessary), for details see Section 16.2.
- Only for subjects in Part 3 in Cycle 2: peripheral blood sample collection for determination of cytokine levels. 
- Calculation of eGFR (see Section 16.9)
- Only on Day 1 of Cycles 2, 3, 4 and 5: Blood (plasma) sample collection for exposure-response modeling at pre-dose and between 0.5 and 1.5 hours post-dose in all subjects participating in the MTD expansion cohorts of study Part 1, Part 2, and Part 3 (not in subjects with impaired renal function), see Table 16-3. The dose needs to be taken under supervision and the time recorded. 
- Only on Day 1 of Cycle 2: Obtain second biopsy: mandatory for all subjects in the MTD expansion cohort of Part 1 (all comer), voluntary for subjects in the dose escalation cohorts of study Part 1 (all comer) and in the MTD expansion cohort of Part 2, and send to laboratory, see Section 16.2.
- Mandatory for all subjects in study Part 3 / MTD expansion "Safety cohort" (sqNSCLC + LAC + BC): Between Day 1 and Day 21 of Cycle 2: Obtain second biopsy

 PK sampling in part 3 added by Amendment 7, see section 15.6.2.22

 Part 3 was added by Amendment 7, see section 15.6.2.23

<sup>70 Modified by Amendment 7, see section 15.6.2.23

No. BAY 1163877 / 16443

17 Oct 2018 Version 8.0 Page: 80 of 395

and send to laboratory, see Section 16.2; obtain peripheral blood for determination of cytokine levels. Subjects in Part 3 will provide one PK sample within 1 hour of biopsy collection in Cycle 2. 

• Dispense of study medication (BAY 1163877) and diary

#### → Administration of BAY 1163877

• Toxicities / AE assessment and recording (if applicable)

#### Day $8 \pm 1$ and Day $15 \pm 1$ (Visits)

- Update of concomitant therapy
- Physical examination
- Ask subject for changes in vision
- Cardiovascular assessment (BP and HR)
- ECOG performance status
- Blood and urine collection for safety laboratory tests (repetitions for controls may be necessary), for details see Section 16.2.
- Only for subjects in Part 3 on Day 15 in Cycle 2: peripheral blood sample collection for determination of cytokine levels.
- Calculation of eGFR (see Section 16.9)
- → Oral administration of BAY 1163877
- Toxicities / AE assessment and recording (if applicable)

#### End of Cycle 2 and every 2nd subsequent Cycle (i.e., end of Cycles 2, 4, 6, 8, 10, 12)

• Send subject to consultant ophthalmologist for ophthalmological examination and review certificate

#### End of Cycle 2 and every 3rd subsequent Cycle (i.e., end of Cycles 2, 5, 8, 11)

• CT scans of the chest, abdomen and pelvis; CT scans of other metastatic lesions as applicable or MRI and documentation of response according to RECIST, v1.1 (see Section 9.3.1)

#### 9.1.2.3.3 Subsequent Cycles (Cycles ≥13)

#### Day 1 (Visit)

Update of concomitant therapy

 Part 3 - Safety cohort - was added by Amendment 7, see section 15.6.2.23

 Added by Amendment 7, see section 15.6.2.23

No. BAY 1163877 / 16443

17 Oct 2018 Version 8.0 Page: 81 of 395

- Physical examination
- Ask subject for changes in vision
- Cardiovascular assessment (BP and HR)
- Measurement of body temperature and body weight
- 12-lead ECG, single reading (see Section 9.5.3.4)
- ECOG performance status
- Blood and urine collection for safety laboratory tests (repetitions for controls may be necessary), for details see Section 16.2
- Calculation of eGFR (see Section 16.9)
- Oral administration of BAY 1163877
- Toxicities / AE assessment and recording (if applicable)

#### Day 11 (Visit)

- Update of concomitant therapy
- Physical examination
- Ask subject for changes in vision
- Cardiovascular assessment (BP and HR)
- ECOG performance status
- Blood and urine collection for safety laboratory tests (repetitions for controls may be necessary), for details see Section 16.2.
- Calculation of eGFR (see Section 16.9)
- Oral administration of BAY 1163877
- Toxicities / AE assessment and recording (if applicable)

#### End of Cycle 14 and every 2nd subsequent Cycle (i.e., end of Cycles 14, 16, 18, ...)

• Send subject to consultant ophthalmologist for ophthalmological examination and review certificate

#### End of Cycle 14 and every 3rd subsequent Cycle (i.e., end of Cycles 14, 17, 21, ...)

• CT scans of the chest, abdomen and pelvis; CT scans of other metastatic lesions as applicable or MRI and documentation of response according to RECIST, v1.1 (see Section 9.3.1)

No. BAY 1163877 / 16443

17 Oct 2018 Version 8.0 Page: 82 of 395

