  In one of the dose escalation cohorts, administration of a single dose of BAY 1163877 using the tablet formulation on Cycle 1, Day -3 followed by solution formulation starting Cycle 1 Day 1 as described above.
- Study Part 2 / MTD expansion (sqNSCLC + LAC + BC + SCCHN): Individual number of 21-day Cycles with continuous BAY 1163877 monotherapy (tablet or solution) until disease progression or as long as clinical benefit is assumed by the investigator or until unacceptable toxicity occurs.
- Study Part 1 (MTD expansion cohort) and Study Part 2 (sqNSCLC + LAC + BC + SCCHN) / "Food Effect Assessment":
   Approximately 8 subjects will receive single doses of BAY 1163877 on Cycle 1, Day -3 (after consumption of a high-fat, high-calorie breakfast) and on Cycle 1, Day 1 (after an overnight fast of at least 8 hours) followed by treatment according to the schedule described above starting on Cycle 1, Day 3.
- Study Part 3 / MTD expansion "Safety cohort" (sqNSCLC + LAC + BC): Individual number of 21-day Cycles with continuous BAY 1163877 monotherapy (tablet) until disease progression or as long as clinical benefit is assumed by the investigator or until unacceptable toxicity occurs. 

Note: Treatment with BAY 1163877 at MTD in Part 1 (expansion cohort "all comer"), Part 2 (expansion cohort sqNSCLC + LAC + BC + SCCHN), and Part 3 (expansion cohort "Safety cohort", sqNSCLC + LAC + BC) can run in parallel.

- Follow-up (FU)
  - End of Treatment (EOT) visit 0-14 days after last dose of BAY 1163877
  - Follow-up (FU) visit at 30-35 days after dose of BAY 1163877

The first screening visit is scheduled within 7 days / within 28 days before administration of the first dose of BAY 1163877. The informed consent form will be signed by the subject before or at the first screening visit (please refer to Section 13.2). The screening period ends just before start of treatment.

The treatment period starts on the day of the first administration of study treatment either on Cycle 1, Day 1 or on Cycle 1, Day -3 ("tablet bridging cohort" and "food effect assessment") and ends with the last day when the study medication is administered in Cycle X. The length of treatment period may vary from subject to subject dependent on the number of individual treatment cycles. A Cycle for this study is defined as 21 days. There will be no break between cycles.

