Electrocardiogram (ECG): 12-lead ECG readings will be performed at screening, on Cycle 1, Days -3 and -2 ("tablet bridging cohort" and "food effect assessment", only), on Cycle 1, Days 1, 2, and 15, thereafter on Day 1 of each subsequent Cycle, and at the EOT visit. In all Cycles and at the EOT visit, ECG readings will be performed as single readings. The time points for ECG readings and further details are provided in Section 9.5.3.4.

Pharmacodynamic (PD) biomarkers: In an attempt to demonstrate the mechanism of action of BAY 1163877 biomarkers will be studied in tissue samples (for details see Section 9.4.4).

Biomarker analysis in tumor tissue: Biomarker analysis will be done at screening for subject stratification in the MTD expansion cohorts (Part 1: all comer; Part 2: sqNSCLC + LAC + BC + SCCHN; Part 3: sqNSCLC + LAC + BC) according to FGFR expression levels / FGFR mutation using either an archival tumor tissue specimen or fresh tumor biopsy material (see Section 7.1.1, inclusion criteria).

Analysis of phospho-extracellular signal-regulated kinase 1/2 levels, (p-ERK1/2) will be done at screening and on Cycle 2, Day 1 for all subjects of study Part 1 and Part 2 who are willing to undergo a biopsy both at screening and on Cycle 2, Day 1. Both biopsies are mandatory for "all comer" subjects included in the MTD expansion cohort of Part 1 (please refer to Section 7.1.1 for details).

Tumor response evaluation: Computed tomography (CT) or magnetic resonance imaging (MRI) of all anatomic regions involved with the disease will be performed at screening (baseline), at the end of Cycle 2 and thereafter every third cycle to assess tumor response using the Response Evaluation Criteria in Solid Tumors, Version 1.1. (RECIST v1.1)(1).

Response evaluation according to RECIST v1.1 can be done up to 5 days after CT / MR scan.

**Recommended Phase II dose (RP2D)**: The dose recommended for Phase II studies with BAY 1163877 will be determined by the investigators and the sponsor (DSMT) at the end of this study (after Part 2) after having reviewed the data from all dose levels evaluated including PK data, overall incidence and severity of AEs, cardiac safety, and amount of MTD.

<sup>36 Part 3 - Safety cohort - was added by Amendment 7, see section 15.6.2.6

<sup>37 Part 3 was added by Amendment 7, see section 15.6.2.6

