#### 9.3.1 Tumor evaluation - response assessment (RECIST)

In *measurable* lesions (i.e., at the primary site, visceral or nodal [in lymph nodes  $\geq$  1,5 cm] lesions), the objective response will be assessed by CT / MRI scan at the EOT visit and documented according to the revised RECIST guideline, Version 1.1 (RECIST, v1.1), see Section 16.8. The assessment will be done by the investigators. No central evaluation is planned for this study.

CT / MRI scans will be performed at the following time points:

- Screening (within 28 days prior to the first dose of BAY 1163877)
- At the end of Cycle 2 and every third subsequent Cycle (beginning with Cycle 5)

Results for these evaluations will be recorded with as much specificity as possible so that pre- and post-treatment results will provide the best opportunity for evaluation of tumor response.

A zero should be recorded when a lesion has completely resolved. Otherwise, disappearance of a lesion cannot be differentiated from a missing value.

The occurrence and location of new lesions should be recorded in the eCRF and the subject's medical records.

In general, the subject's best response assignment will depend on the achievement of both measurement and confirmation criteria (see Section 16.8).

If radiographic changes are believed by the investigator to be secondary to drug induced inflammation and not tumor progression, the investigator may postpone a diagnosis of progressive disease (PD) until the next radiographic evaluation in the study.

All scans should be done with the identical modality (CT or MRI) and the identical technique (e.g., slice thickness, field of view) to those obtained at baseline. For a response to be scored as complete response (CR) or partial response (PR), the response must be confirmed by a repeat CT scan (with contrast) or MRI scan (with and without contrast) performed not earlier than 4 weeks after the response was first determined.

No. BAY 1163877 / 16443

17 Oct 2018 Version 8.0 Page: 85 of 395

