#### 10.4.7 Efficacy data

Efficacy data, such as best tumor response, will be summarized using descriptive statistics and will be graphically displayed if appropriate. The correlation between pharmacodynamic parameters and selected safety, efficacy, or PK parameters may be graphically displayed. Further statistical analyses may be conducted.

The efficacy analysis will include descriptive analyses on response rate, progression-free survival (PFS) and time to progression (TTP).

**Response** as defined by RECIST v.1.1: complete response (CR), partial response (PR), stable disease (SD), progressive disease (PD), see Section 16.8.

**Progression-free survival (PFS)** is defined as the time (days) from the date of the first dose of study drug to the date of the first observed radiological disease progression or death, whatever comes first. PFS for subjects without tumor progression at the time of analysis will be censored at their last date of tumor evaluation.

**Time to progression (TTP)** is defined as the time from start of study treatment until objective tumor progression; TTP does not include deaths.

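### The scan list for Cycle 13 onward reads 14, 17, 21, but the every-third-cycle rule in the same line gives 14, 17, 20

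*Protocol*

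**What the plan says.** The protocol states the tumor imaging rule in several places in its current text:

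- Section 6, in the paragraph on tumor response, requires imaging "at the end of Cycle 2 and thereafter every third cycle to assess tumor response". Section 9.4.4 repeats this.
- Section 9.1.2.3.2 (Cycles 2 to 12) gives the same rule and lists the time points as "subsequent Cycle (i.e., end of Cycles 2, 5, 8, 11".
- Section 9.3.1 says "At the end of Cycle 2 and every third subsequent Cycle (beginning with Cycle 5".
- Section 9.1.2.3.3 (Cycle 13 onward) names Cycle 14 and every third cycle after it, then lists "subsequent Cycle (i.e., end of Cycles 14, 17, 21", followed by an ellipsis.

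Two statements in Section 6 convert cycles to calendar time: "A Cycle for this study is defined as 21 days" and "There will be no break between cycles".

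Scan dates enter the efficacy results through Section 10.4.7. PFS ends at the first radiological progression or death, and "PFS for subjects without tumor progression at the time of analysis will be censored at their last date of tumor evaluation". TTP ends at objective progression.

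**The concern.** The line in Section 9.1.2.3.3 gives a rule and then a list meant to say the same thing, and the two differ at the third entry. A site could scan after Cycle 20 on the strength of the rule, or after Cycle 21 on the strength of the list, and each could point to the protocol.

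Progression found by imaging is dated at the scan, so the interval between scans limits how precisely it can be dated. Section 9.3.1 leaves the assessment to the investigators and plans no central evaluation. If sites read the line differently, two subjects with the same disease course could get different PFS and TTP dates for no clinical reason.

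**Working it through.** **Inputs.** The cycle length is 21 days with no break between cycles (Section 6). Scans are due at the end of Cycle 2 and then every third cycle (Sections 6, 9.1.2.3.2, 9.3.1 and 9.4.4). The printed lists are 2, 5, 8, 11 (Section 9.1.2.3.2) and 14, 17, 21 (Section 9.1.2.3.3).

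**Step 1: can the printed 21 be reproduced?**

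- Counting from Cycle 2, the scan cycles are 2 + 3k. For k = 0 to 7 this gives 2, 5, 8, 11, 14, 17, 20, 23. Reaching 21 would need k = 19/3, which is not a whole number.
- Starting afresh at Cycle 14, the scan cycles are 14 + 3k: 14, 17, 20, 23. Reaching 21 would need k = 7/3, again not a whole number.

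Neither starting point gives 21.

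**Step 2: do the neighboring lists follow their own rules?** The list for Cycles 2 to 12 has steps of 3, 3 and 3, as its rule requires. The ophthalmology list, also in Section 9.1.2.3.3, reads "subsequent Cycle (i.e., end of Cycles 14, 16, 18". Its steps are 2 and 2, which fits its rule of every second cycle. Of these lists, only the scan list for Cycle 13 onward fails, with steps of 3 and 4.

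**Step 3: the intervals in days** (cycles × 21).

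| Interval | Cycles | Days | Weeks |
|---|---|---|---|
| 2–5, 5–8, 8–11, 11–14, 14–17 | 3 each | 63 each | 9 each |
| 17–20, by the rule | 3 | 63 | 9 |
| 17–21, as printed | 4 | 84 | 12 |

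Counted from Cycle 1, Day 1, Cycle 17 ends on day 17 × 21 = 357 (week 51), Cycle 20 on day 420 (week 60) and Cycle 21 on day 441 (week 63).

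**Step 4: the effect on dating.** Progression that arises between the ends of Cycles 17 and 20 is seen at day 420 under the rule and at day 441 under the list. The difference is 441 − 420 = 21 days. It is smaller if an unscheduled scan finds the progression first.

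**Step 5: what happens after Cycle 21?** Nothing is printed after 21. Assume, for illustration, that a site following the list goes on in threes (21, 24, 27) while the rule gives 20, 23, 26.

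| Onset between the ends of Cycles | Found, rule | Found, list | List minus rule |
|---|---|---|---|
| 20 and 21 | 23 | 21 | −2 × 21 = −42 days |
| 21 and 23 | 23 | 24 | +1 × 21 = +21 days |

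If onset is spread evenly over these three cycles, the mean shift is (1 × (−42) + 2 × 21) / 3 = 0. The pattern repeats every three cycles. On this assumption the shifted schedule causes no systematic delay beyond the single 17–21 interval.

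**The case against.** The best answer is that this is a one-digit slip in an illustrative list. The governing rule is stated correctly in four other sections and in the very line that contains the slip. The bullet under that line refers the reader to Section 9.3.1, which is right. A careful site would probably scan after Cycle 20. This argument stands as to severity, but the line still gives two different instructions.

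It is also tempting to call this list the operative one, the list that sites actually follow. The documents do not support that. Section 9.1 refers to the flow charts in Section 16.1 for the tabulated schedule and the visit windows, and those charts are not in the text available here. The 84-day gap therefore arises only if a site follows the printed list.

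A reader might also infer that all later scans shift by one cycle and that late progression is recorded late throughout. The document prints nothing after 21, and even if the list runs on in threes, earlier and later detection balance from Cycle 20 onward, as the working shows. Only the 17–21 interval gives a one-directional delay.

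Finally, the effect on the results is small. Efficacy is a secondary endpoint (Section 9.3), PFS and TTP are described only (Section 10.4.7), and no confirmatory analysis is planned (Section 10.1). Section 6.2 expects most subjects to live about 3 months, so few should still be on treatment past week 51, although the protocol gives no count. Section 9.3.1 also lets an investigator who suspects drug-induced inflammation hold back a diagnosis of progression until the next scan. That is nominally 63 days, three times the 21 days at issue. All of this stands, and it is why the point is minor.

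**Conclusion.** Section 9.1.2.3.3 contradicts itself: the rule gives 14, 17, 20 and the list says 14, 17, 21. The error is in current protocol text, in a schedule written for sites. Sections 6, 9.1.2.3.2, 9.3.1 and 9.4.4 state the rule correctly; they are evidence of what was meant and not further places where the error occurs.

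If a site follows the list, one interval is 84 days where the rule gives 63, and progression arising between the ends of Cycles 17 and 20 is recorded up to 21 days later than at a site following the rule. This reaches only subjects treated beyond Cycle 17, about 51 weeks, and only the descriptive secondary PFS and TTP. The figures assume that cycles run on the nominal 21-day calendar and that progression is found at a scheduled scan.

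The documents do not show that any site scans after Cycle 21, that detection is delayed in general after Cycle 17, or that the PFS and TTP summaries as a whole are at risk.

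**What to change.** In Section 9.1.2.3.3, change the third entry of the CT/MRI list from 21 to 20, so that it reads 14, 17, 20 and continues in threes. That is the only list consistent with the rule as the protocol states it throughout. Check the treatment flow chart in Section 16.1 (Table 16-3) for the same figure and align it if needed.

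The cost is one figure, and it can go into the next amendment. If subjects have already been treated past Cycle 17, confirm with the sites which scan cycle they used, so that any 84-day interval is known when late PFS and TTP dates are read.

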#### 9.1.2.3.4 Follow-up

An End of Treatment (EOT) visit will be performed within 0-14 days after the last study drug administration.

A follow-up (FU) visit will be performed 30-35 days after the last study drug administration. This will be a visit for subjects who have not started a new treatment. For subjects who have started a new antitumor treatment, only a phone call will be made. There will be no long-term (survival) follow-up period.

The following examinations will be done

#### Within 0-14 Days of Last Study Drug Administration (EOT Visit)

- Update of concomitant therapy
- Return of study medication and diary
- Physical examination
- Ask subject for changes in vision
- Cardiovascular assessment (BP and HR)
- Measurement of body temperature and body weight
- 12-lead ECG, single reading (see Section 9.5.3.4)
- ECOG performance status
- Blood and urine collection for safety laboratory tests (repetitions for controls may be necessary), for details see Section 16.2.
- Calculation of eGFR (see Section 16.9)
- Send subject to consultant ophthalmologist for ophthalmological examination and review certificate
- Toxicities / AE assessment and recording (if applicable)

#### At 30-35 days after last study drug administration: FU (Visit / Phone call)

#### If FU-visit:

- Physical examination
- Ask subject for changes in vision
- Cardiovascular assessment (BP and HR)
- Toxicities / AE assessment and recording (if applicable)

#### If FU-phone call\*

Toxicities / AE assessment and recording (if applicable)

\*For subjects who have started a new antitumor treatment.

No. BAY 1163877 / 16443

17 Oct 2018 Version 8.0 Page: 83 of 395

#### 9.2 Population characteristics

#### 9.2.1 Demographic

The following information will be collected and summarized as part of the demographic and baseline characteristics for all subjects enrolled in this study: age, gender, ethnic group. The subjects of all races / ethnicity can participate in the study provided that they meet all eligibility criteria.

